Oui Therapeutics, Inc. | [name]

Assessment	Construct	Description
User feedback questions	Usability	All stakeholders will answer open-ended questions related to the eYST website features to obtain feedback regarding the social support program for future improvements.
Suicide Ideation Questionnaire Jr (SIQ-JR)	Suicide Ideation	The SIQ - JR is a 15-item, validated self-report scale that is part of the PhenX Toolkit (Reynolds, 1987). It assesses suicidal thoughts over the past month. Items are rated on a 0-6 scale that captures the frequency of the thoughts of adolescents.
Patient Health Questionnaire-2 (PHQ-2)	Depression	The PHQ-2 is a self-administered and validated tool to measure depressive symptoms (Kroenke et al., 2003). The PHQ-2 inquires about the frequency of depressed mood and anhedonia over the past two weeks. The PHQ-2 includes the first two items of the PHQ-9 (Kroenke et al., 2001).
Family, School, and Peer Connectedness (FSPC)	Connectedness	We will use the three 2-item scales to assess Family, Peer and School connectedness, which have shown predictive validity for adolescent suicide attempt outcomes ([name], Grupp-Phelan, et al., 2019). This brief scale was adapted from the previously validated Parent-Family Connectedness Scale (Resnick et al., 1997), the School Connectedness Scale (Resnick et al., 1997) and the Adolescent Connectedness Scale (Karcher & Sass, 2010).
Social Provisions scale (SPS)	Connectedness	Connectedness will be assessed using the validated SPS (Cutrona & Russell, 1987). This scale is a 24-item scale that consists of six subscales to measure the availability of social support: emotional support or attachment, social integration, reassurance of worth, tangible help, orientation, and opportunity for nurturance.
Sources of Strength Coping Scale	Connectedness	The Sources of Strength Coping Scale (Wyman et al., 2010) assesses the extent to which youth view resources (e.g. family, friends, adult mentors, services, etc.) as helpful to them. We will use this scale to assess adolescents' perceptions of the availability of guidance, attachment, and reassurance of worth from adults in their lives.

PROPRIETARY AND CONFIDENTIAL

Oui Therapeutics, Inc. | [name]

Assessment	Construct	Description

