10.8 SAFETY MONITORING AND REPORTING

PROPRIETARY AND CONFIDENTIAL

Oui Therapeutics, Inc. | [name]

Suicidal ideation/behaviors and other clinical outcomes will be assessed at the Week 0 and Week 12 follow-up assessments. Week 0 is the study baseline assessment, which occurs while the participant is housed in an inpatient treatment facility. For purposes of risk management, results of the study assessment at Week 0 will be shared with the inpatient treatment team in order to provide information relevant to their treatment/discharge planning. The 12 week follow up assessment is conducted by phone. In order to facilitate risk management during study interview calls, we will do the following:

- 1) Only enroll participants who are able to provide at least one verifiable contact for emergency or tracking purposes;
- 2) Obtain location information at the start of each phone assessment; and
- 3) Schedule assessments at a time when the parent/guardian is present at the same location as the participant.

Each youth assessment session will begin by confirming via telephone/video whether the youth and guardian are together. Increases in suicide risk will be communicated to the parent/guardian and outpatient provider (see Appendix B). In addition, interviewers will engage in risk management interventions as clinically indicated following the guidelines outlined in the Risk Management Plan (see Appendix B). Participants will be informed that information they input to the digital platform is not monitored for purposes of risk assessment.

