12.1.2 Rationale

A single arm design (vs. a controlled design) is appropriate as the workflow for eYST has not been implemented elsewhere. At the end of this study, we will know how to support implementation fidelity, which is key for a future RCT.

Missing data: For missing post-tests, we will use a last observation carried forward imputation, as more sophisticated missing data methods are not appropriate for our sample size.

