12.1.3 Justification of sample size-suicide attempts

No power calculation was used to determine sample size because this is an exploratory feasibility study ([Jones et al., 2003](#)). Research shows that 5 participants are sufficient to detect 80% of usability issues ([Bailey, 2005](#); [Nielsen & Faber, 1996](#)) and 15 are sufficient to detect serious usability issues ([Spool & Schroeder, 2001](#)). Therefore, we plan to recruit 20 youth participants, accounting for dropouts.

We will not make conclusive statements about intervention effects due to the small sample size, the single arm design and the fact that clinical improvement may be expected with the passage of time (i.e., without eYST), especially post inpatient admission.

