12.1.5 Secondary Endpoints

Analysis of our exploratory outcomes associated with YST including suicidal thoughts and behaviors, healthcare service utilization, and perception of social support will be conducted only to document the extent and variation of change across subjects. The results of these analyses will be interpreted with great caution given the small sample size and single arm design. Clinically Significant Change (CSC) is a metric that can be applied to assess within patient change at the individual level. We will document the percentage of participants who experience CSC from baseline to 12 weeks on the outcomes of interest using procedures described by Morley and Dowzer ([Morley & Dowzer, 2014](#)). We will compare patterns of change from baseline to follow-up periods to parallel data from a former RCT of YST ([[name] et al., 2009](#)).

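### Carrying baseline forward scores each youth missing week 12 as exactly unchanged, which lowers the exploratory clinically-significant-change percentages by the factor (20−m)/20

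*Combined protocol and SAP*

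**What the plan says.** Section 12.1.2 sets one missing-data rule: "For missing post-tests, we will use a last observation carried forward imputation". Its reason is that this is preferable "as more sophisticated missing data methods are not appropriate for our sample size".

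Section 12.1.5 applies to the exploratory clinical outcomes: "We will document the percentage of participants who experience CSC from baseline to 12 weeks on the outcomes of interest". It continues: "We will compare patterns of change from baseline to follow-up periods to parallel data from a former RCT of YST". It plans no confidence interval or test for the CSC percentage, and it does not say whether improvement and deterioration will be shown separately.

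On timing, Section 10.8 says: "Suicidal ideation/behaviors and other clinical outcomes will be assessed at the Week 0 and Week 12 follow-up assessments". Table 1 (Section 1.3) agrees: the SIQ-JR, PHQ-2, FSPC, SPS and Sources of Strength rows are marked for youth at W0 and W12 and are blank between.

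On the course expected, Section 12.1.3 warns that "clinical improvement may be expected with the passage of time (i.e., without eYST), especially post inpatient admission".

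**The concern.** With two measurement times, last observation carried forward is the same as setting follow-up equal to baseline. A lost youth and a youth seen to be unchanged are then scored alike. Section 12.1.5 is meant to describe how much youth change and how far they differ from one another, and inserted zeros distort both.

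Zero change is also a poor default here. Section 10.8 says that "Week 0 is the study baseline assessment, which occurs while the participant is housed in an inpatient treatment facility", Section 8.1 says of the SIQ-JR that "It assesses suicidal thoughts over the past month", and Section 12.1.3 itself expects improvement after admission. The reason given for the rule does not settle the matter, because counting the youth who were observed is simpler than imputing.

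At stake are the descriptive CSC percentages, the mean changes, and the comparison with the former randomised trial of YST. The usability benchmark (SUS) does not depend on them.

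**Working it through.** **Inputs.** N = 20 youth (Sections 7 and 12.1.3). Measurement at weeks 0 and 12 only (Table 1; Section 10.8). The number missing at week 12, m, is not given. Section 12.1.3 allows for dropouts without stating a rate. I assume m = 1 to 5; at m = 5 the observed number is 20 − 5 = 15, a size that section also mentions. The counts of changers below are assumed too. There is no power calculation or planned CSC figure to reproduce.

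**Step 1: the imputed change.** Imputed week 12 = baseline, so change = 0. Zero cannot pass any reliable-change threshold, so the youth is non-CSC.

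**Step 2: effect on a share.** Let k of the n = 20 − m observed youth meet the criterion.

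- Observed share = k/n.
- Carried-forward share = k/20 = (k/n) × (20−m)/20.
- Possible share of all 20 = k/20 to (k+m)/20. The rule always reports the low end.

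| m | n | factor = ceiling on CSC | exact 95% upper limit for 0/n | for 0/20 |
|---|---|---|---|---|
| 1 | 19 | 0.95 | 17.6% | 16.8% |
| 2 | 18 | 0.90 | 18.5% | 16.8% |
| 3 | 17 | 0.85 | 19.5% | 16.8% |
| 4 | 16 | 0.80 | 20.6% | 16.8% |
| 5 | 15 | 0.75 | 21.8% | 16.8% |

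Example, m = 5 and k = 9: observed 9/15 = 60.0% (Clopper-Pearson 32.3 to 83.7); carried forward 9/20 = 45.0% (23.1 to 68.5); possible range 9/20 = 45% to 14/20 = 70%.

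**Step 3: effect on mean change.** Mean over 20 = (n × observed mean + m × 0)/20, which is the observed mean times (20−m)/20.

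**Step 4: effect on precision.** The direction depends on the rate. Clopper-Pearson widths, in percentage points:

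| Observed | width | Carried forward | width |
|---|---|---|---|
| 9/15 = 60.0% | 51.4 | 9/20 | 45.4 |
| 12/15 = 80.0% | 43.8 | 12/20 | 44.8 |
| 14/15 = 93.3% | 31.8 | 14/20 | 42.4 |
| 16/19 = 84.2% | 36.2 | 16/20 | 37.9 |

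The interval on 20 is narrower at low to moderate rates and wider once the observed rate passes roughly 70 to 80%.

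Mean change behaves likewise. With d = observed mean/SD of change, the ratio of the carried-forward standard error to the observed one is √n × √{[(n−1) + n·d² − 20·(n·d/20)²]/(19 × 20)}. At d = 0.5, 1.0, 1.5 and 2.0 it is 0.77, 0.84, 0.94 and 1.07 for m = 5, and 0.95, 0.97, 1.00 and 1.04 for m = 1.

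**The case against.** The strongest reply is that little turns on this. The outcomes are exploratory, Section 12.1.3 rules out conclusive statements about effects, and Section 12.1.5 promises cautious interpretation. Sections 8.6, 8.7 and 12.2 describe retention efforts, a week-12 payment and attempts to obtain final assessments. With one youth missing, no share moves by more than 5 points. For improvement, the rule errs on the cautious side. All of this stands and keeps the priority low. However, the promised caution is tied to sample size and the single arm, not to imputation, and retention can reduce m without changing how those still missing are scored.

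A second reply is that Section 12.1.1 promises to report completion of assessment appointments, so a reader could recover k/(20−m). That works only in part, because completion need not be given scale by scale.

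Third, the inpatient baseline is not universal: Sections 4.1, 5 and 7 allow recruitment or enrolment after discharge. That weakens the argument that zero change is implausible for some youth but leaves the arithmetic untouched.

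Fourth, an observed-only share describes completers and can be biased as well. This is correct, and is why the possible range belongs beside it.

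A reader might also infer that the rule always makes results look more precise. It does not: Step 4 shows wider intervals at high rates, and the plan states no interval at all.

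**Conclusion.** The point holds as a low-priority improvement. For the five youth scales measured only at weeks 0 and 12, the stated rule treats unknown values as known and turns a missing week-12 score into exact non-change. The CSC share and the mean change are multiplied by (20−m)/20, which is 0.95 to 0.75 for an assumed m of 1 to 5, and the share reported is the lowest possible for the 20. The factor follows from the documents; its size in practice rests on m, which they do not give.

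A reader might infer that the plan will understate deterioration. That would follow only if a deterioration share is reported: it would then be diluted by the same factor, and the low end is not the cautious end for that outcome. Section 12.1.5 names a single CSC percentage, and whether the cited reliable-change manual splits it by direction cannot be checked here. Nor is safety oversight weakened, since it runs through the C-SSRS and adverse event monitoring (Sections 8.1 and 10). No primary or secondary conclusion changes.

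**What to change.** - **Section 12.1.2:** do not carry the last observation forward for outcomes measured only at weeks 0 and 12.
- **Section 12.1.5:** for each such outcome on which CSC is computed, report CSC among youth with an observed week-12 score, with the number observed. Show the number missing as a separate row and give the possible range k/20 to (k+m)/20. Show improvement and deterioration separately if the CSC procedure yields both.
- **Comparison with the former trial:** state the number observed, and match that trial's handling of missing scores where it is known. The documents do not describe it, so observed scores should not be assumed to be the more comparable choice.

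The cost is a few sentences and an extra table row, with no new data. The downside is a smaller denominator and an estimate for completers only, which the missing row and the range make visible. If nobody is missing, the results are the same as under the present rule.

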12.1.3 Justification of sample size-suicide attempts

No power calculation was used to determine sample size because this is an exploratory feasibility study ([Jones et al., 2003](#)). Research shows that 5 participants are sufficient to detect 80% of usability issues ([Bailey, 2005](#); [Nielsen & Faber, 1996](#)) and 15 are sufficient to detect serious usability issues ([Spool & Schroeder, 2001](#)). Therefore, we plan to recruit 20 youth participants, accounting for dropouts.

We will not make conclusive statements about intervention effects due to the small sample size, the single arm design and the fact that clinical improvement may be expected with the passage of time (i.e., without eYST), especially post inpatient admission.

12.1.5 Secondary Endpoints

Analysis of our exploratory outcomes associated with YST including suicidal thoughts and behaviors, healthcare service utilization, and perception of social support will be conducted only to document the extent and variation of change across subjects. The results of these analyses will be interpreted with great caution given the small sample size and single arm design. Clinically Significant Change (CSC) is a metric that can be applied to assess within patient change at the individual level. We will document the percentage of participants who experience CSC from baseline to 12 weeks on the outcomes of interest using procedures described by Morley and Dowzer ([Morley & Dowzer, 2014](#)). We will compare patterns of change from baseline to follow-up periods to parallel data from a former RCT of YST ([[name] et al., 2009](#)).

12.2 ADDITIONAL CONSIDERATIONS

Staff training at study initiation

1. Trained/Designated Staff: There will be designated research staff who will be trained to collect study outcomes.

PROPRIETARY AND CONFIDENTIAL

Oui Therapeutics, LLC Aviva (OTX-2021)	Digital Youth-Nominated Support Team (YST) Program	Informed Consent Form Clean Copy Page 33
---	---	---

2. **Clear Definitions and Electronic Data Capture:** We will use a structured method for obtaining all study outcomes. For variables assessed, there will be clear definitions. Staff will receive training in how to apply those definitions and record them in the study electronic data capture (EDC) system.

During study monitoring and support

1. **Study Monitoring and Data Fidelity Checks:** The sponsor or its representative may visit the study facilities at any time (remotely and /or in person) in order to maintain current and personal knowledge of the study through review of the records, comparison with source documents, observation and discussion of the conduct and progress of the study. The clinical site will permit trial-related monitoring, audits, IRB/IEC review, and regulatory inspection(s) by providing direct access to source data/documents.
2. **Fidelity Checks:** As part of study monitoring, we will conduct ongoing fidelity checks for the primary outcomes (and other variables of interest). During fidelity checks, records will be pulled randomly. If errors in coding the variables are observed, the nature of the error will be evaluated to determine whether study procedures need to be updated to improve clarity (though unlikely as we are using methodologies established in prior work) and/or staff require additional training in how to capture the study variables.

Procedures for participants who drop out or are lost to follow-up

If subjects drop out or are lost to follow-up, there will be agreements with the subject per the Informed Consent that the research staff can access different sources of information other than medical records. Additional sources of information will be the persons listed as individuals the research staff may reach out to if the research staff cannot contact the participants. The study team may also attempt to obtain final study assessments if possible before withdrawal of consent, as previously mentioned in Section 9.2 Participant Discontinuation/Withdrawal From The Study.

13. APPROACH TO ENSURE INTEGRITY OF DATA TO SUPPORT PRIMARY ENDPOINTS

13.1 REDUCE LIKELIHOOD OF INACCURATE OR BIASED PATIENT REPORTS DURING ASSESSMENTS

- Participants will be instructed to schedule their phone call during a time when they are free from distractions and can provide reliable and accurate responses.
- Data will be collected by research staff or via the eYST platform. The Clinicians (PIs) may be responsible for patient care during study participation, so having independent research staff helps mitigate the risk of potential bias.

13.2 REDUCE LIKELIHOOD OF STAFF DEVIATING FROM THE DATA COLLECTION PROTOCOL

- The data collectors will be trained on conducting the interviews and recording data. The training may include role-playing and simulations. Training will cover how to respond to adverse events.

PROPRIETARY AND CONFIDENTIAL

Oui Therapeutics, Inc. | [name]

- The data safety and monitoring plan will be shared with the clinicians. For example, they will be trained on how to differentiate an active suicide crisis from a person who has suicide intent.
- Data collectors will receive ongoing supervision.
- The study team will make appointments for assessments when there will not be distractions for the participants.
- The EDC system will be programmed to validate data where feasible to ensure accurate reporting and to reduce data entry errors and incomplete data

14. DATA SECURITY FOR EYST

14.1 CYBERSECURITY AND DATA COLLECTION

Participant data (including electronic consent forms) will be stored on Michigan Medicine's HIPAA compliant servers. Participants will be given an identification number, which will be matched to participant names in a password-protected electronic document, which will only be accessible to IRB-approved study staff. Only coded, de-identified data will be shared with our company through secure data transfer.

The team at Oui has developed and implemented certain measures to ensure cybersecurity and data protection on previous digital platforms. eYST is built on the fundamental principle of anonymity with security and privacy engineered into the core design. This includes (1) applying a security framework, and (2) ensuring data segregation of Protected Health Information (PHI). The data will not retain participant names when entered into our system and will only be accessible by authorized users. Our measures to ensure cybersecurity and data protection include:

- 1) Unique password-protected user accounts.
- 2) Detailed user account enrollment. When users begin the enrollment process and have provided their access code, they will be prompted to fill in their identity information, including their name, date of birth, email address, etc., and a personal password to protect their account. The combination of both their enrolled phone number and personal password will authorize them access to the application on a supported mobile device.
- 3) Strong password requirements. User passwords will be required to be 8 or more characters in length.
- 4) Security and penetration testing.

14.2 SECURITY CULTURE

The technology group's primary tool to ensure security for the users will be by starting with a security culture. All server-side processes will be run in docker containers with minimal privileges. Access to non-development environments will be restricted to a few employees and our policy will require it to be used only in emergency measures and with oversight.

14.3 COMMUNICATION

Connectivity to and within eYST will be severely restricted, and all communication will be encrypted.

PROPRIETARY AND CONFIDENTIAL

Oui Therapeutics, Inc. | [name]

Oui Therapeutics, LLC Aviva (OTX-202)	Digital Youth-Nominated Support Team (YST) Program	Informed Consent Form Clean Copy Page 35
--	---	---

14.4 ROLE-BASED PRODUCTION ACCESS

Access across all deployment tiers (development, beta, production) leverages a role-based entitlement system that associates privileges with a certain role, which will be then associated with appropriate users to ensure comprehensive access management.

14.5 DATA ENCRYPTION

All personally-identifiable information will be decrypted only in-memory and encryption keys provide a second check on access controls.

eYST data is stored using Google Cloud Platform which ensures that all our data is encrypted in transit and at rest.

14.6 AUDITING

All activity within, access of, and attempted access of eYST will be monitored, logged, and stored for anomaly detection and auditing.

14.7 TESTING

eYST will be declaratively provisioned and will have an extensive testing process run with automated scripts.

15. DIRECT ACCESS TO SOURCE DATA/DOCUMENTS

Direct access will be granted to authorized representatives from the sponsor, host institution and the regulatory authorities to permit trial-related monitoring, audits and inspections.

16. QUALITY CONTROL AND QUALITY ASSURANCE PROCEDURES

The study will be conducted in accordance with the current approved protocol, ICH GCP, relevant regulations and standard operating procedures. Regular monitoring will be performed according to ICH GCP. Data will be evaluated for compliance with the protocol and accuracy in relation to source documents. Following written standard operating procedures, the monitors will verify that the clinical trial is conducted, and the data generated, documented and reported in compliance with the protocol, GCP and applicable regulatory requirements.

18. ETHICS

18.1 DECLARATION OF HELSINKI

The Investigator will ensure that this study is conducted in accordance with the principles of the Declaration of Helsinki.

18.2 ICH GUIDELINES FOR GOOD CLINICAL PRACTICE

The Investigator will ensure that this study is conducted in full conformity with relevant regulations and with the ICH Guidelines for Good Clinical Practice (CPMP/ICH/135/95) July 1996.

